Appendix A. Technical Detail and Supplemental Information Regarding
Statistical Procedures and Programs 37

Appendix B. Reference Values/Toxicity Grades 39

Table of Abbreviations

Abbreviation/Acronym	Definition
ADPC	Analysis Dataset for PK Concentrations
AE	Adverse Event
AMQs	Amgen MedDRA Queries
CDM	Clinical Data Management
CR	Complete Response
CPMS	Clinical Pharmacology Modeling and Simulation
CRF	Case Report Form
CSR	Clinical Study Report
CTCAE	Common Terminology Criteria for Adverse Events
DLBCL	Diffuse Large B-Cell Lymphoma
DLRT	Dose Level Review Team
DRT	Data Review Team
DLT	Dose Limiting Toxicity
DOR	Duration of Response
DRE	Disease Related Events
ECG	Electrocardiogram
ECI	Event of Clinical Interest
EOI	Events of interest
E-R analysis	Exposure Response Analysis
FAS	Full Analysis Set
GSO-DM	Global Study Operations-Data Management
HSCT	Hematopoietic Stem Cell Transplantation
IA	Interim Analysis
IP	Investigational Product
IPD	Important Protocol Deviations
IPI	International Prognostic Index
IVRS	Interactive Voice Response System
KM	Kaplan-Meier
MedDRA	Medical Dictionary for Regulatory Activities
MTD	Maximum Tolerated Dose
NGS	next generation sequencing
OR	Objective Response
ORR	Objective Response Rate
OS	Overall Survival

Abbreviation/Acronym	Definition
PFS	Progression Free Survival
PK	Pharmacokinetics
PR	Partial Remission
SAP	Statistical Analysis Plan
SMQs	Standard MedDRA Queries
SSAP	Supplemental Statistical Analysis Plan
WHODRUG	World Health Organization Drug

1. Introduction

The purpose of this Statistical Analysis Plan (SAP) is to provide details of the statistical analyses that have been outlined within the protocol amendment **5** for the phase 1b blinatumomab in combination with pembrolizumab study 20150290, dated **December 03, 2019**. The scope of this plan includes the primary analysis and the final analysis that is planned and will be executed by the Global Biostatistics Science department unless otherwise specified. Pharmacokinetic, pharmacodynamic, exposure-response and biomarker analyses will be performed by Clinical Pharmacology Modeling and Simulation (CPMS) or biomarker group.

2. Objectives

2.1 Primary

To determine the maximum tolerated dose (MTD) of blinatumomab in combination with pembrolizumab in adult subjects with relapsed or refractory (r/r) diffuse large B-cell lymphoma (DLBCL).

2.2 Secondary

To evaluate the safety, efficacy, and pharmacokinetics (PK) of blinatumomab in combination with pembrolizumab in adult subjects with r/r DLBCL

2.3 Exploratory

- To evaluate blood and tissue biomarkers
- To evaluate minimal residual disease (MRD) response by next generation sequencing (NGS)

3. Study Overview

3.1 Study Design

This is an open label, multicenter, phase 1b study testing the combination of blinatumomab with pembrolizumab in r/r DLBCL.

The study will consist of 2 portions:

- Part 1 (n = 6 – **30**) will test the safety of up to 3 different blinatumomab target dose levels in combination with pembrolizumab in a rolling 6 design. A Dose Level Review Team (DLRT) will review the safety data to evaluate possible drug effects and dose limiting toxicities (DLTs). Subjects who are not on the dose ultimately selected for part 2 will remain on their initial dose throughout the study.
- Part 2 (n = **40**) will consist of an expansion cohort to assess PK, safety, and preliminary efficacy data at the chosen target dose. The part 2 dose will be determined by the totality of the clinical data from part 1 as determined by the DLRT.

The study design includes:

- A 21-day screening period.
 - A standard (core) treatment period of blinatumomab (first cycle) of 8 weeks
 - A second (consolidation) cycle of blinatumomab of 28 days after a 28-day (± 3 days) blinatumomab treatment-free period that can be administered to subjects with stable disease (SD), partial **remission** (PR), or complete **remission** (CR).
 - Pembrolizumab treatment until disease progression **or relapse** or up to 35 cycles in the absence of disease progression **or relapse**:
 - **To begin** on study day 15 for subjects in cohort Ia
- OR
- **To begin** on study day 19 for subjects in cohort IIa and IIIa
- A safety follow-up visit after 30 days (+ 7 days) of last dose of each protocol specified therapy.

Follow-up for survival and collection of subsequent anticancer therapies will occur every 12 weeks (± 28 days) following blinatumomab safety follow-up visit for **until** approximately 24 months from the last dose of pembrolizumab.

Part 1 design and blinatumomab escalation/de-escalation rules

For part 1, subject enrollment will start in cohort Ia as outlined in the schema in [Figure 1](#). Blinatumomab will be dosed as a continuous intravenous infusion (CIVI) for 8 weeks. The initial dose will be 9 $\mu\text{g}/\text{day}$ and the dose will be escalated after 7 days to a target dose of 28 $\mu\text{g}/\text{day}$. Depending on tolerability, the target dose of blinatumomab will be increased to a maximum of **56** $\mu\text{g}/\text{day}$ in cohort IIa **or** to **112** $\mu\text{g}/\text{day}$ in cohort IIIa. Pembrolizumab will be dosed by intravenous (IV) infusion 200 mg at Q3W starting on study day 15 in cohort Ia, and on study day 19 in cohorts IIa and IIIa. Trial treatment of pembrolizumab may be administered up to 3 days before or after each scheduled day 1 from pembrolizumab cycle 2 onwards.

Subjects who do not meet the criteria for investigational product (IP) discontinuation (see below) are eligible for a second cycle of blinatumomab (consolidation) consisting of a CIVI of 28 days after a 28-day (± 3 days) blinatumomab treatment-free interval. Blinatumomab will be started at 9 $\mu\text{g}/\text{day}$ and escalated every 7 days to the maximum target dose of blinatumomab in the assigned cohort.

Subjects will be enrolled to part 1 with up to 6 subjects being enrolled per cohort. In any cohort, tolerability **will be defined as ≤ 1 DLT out of 6 subjects**). **Expansion** to 10 subjects **will be allowed in any cohort** to ensure adequate safety and PK data is

collected. The decision to expand a cohort will be made by the DLRT. **In case of 10 subjects enrolled, tolerability is defined as ≤ 2 DLTs out of 10 subjects.**

The MTD of blinatumomab will be defined as the **highest** dose level at which at most 1 of 6 subjects **or at most 2 subjects in 10** experiences a DLT. The MTD defines the stopping rules for the study. For further details on replacement of subjects is given in Section 3.4 of protocol. The DLT criteria are defined in the Appendix E of the protocol.

The DLRT will meet to review the safety data when any of the following criteria are met:

- In two or more subjects **out of 6, a DLT has been reported, or 3 or more subjects out of 10, a DLT** has been reported in a cohort.
- Six subjects are enrolled in a cohort and all subjects have completed the DLT observation period.
- In the event that a cohort is expanded to 10, DLRT **will** also meet after all subjects have completed DLT observation period.

The DLRT will review the available data in part 1 to determine if the combination of blinatumomab and pembrolizumab is safe and tolerable as defined by DLT criteria.

Based on the totality of the data, the DLRT may recommend **MTD, to escalate to the next dose level, or** to expand a cohort to a maximum of 10 subjects if the collection of more data is deemed warranted, **or to adjudicate DLT criteria (see Appendix E of protocol for details). At the end of Part 1, the cohort with recommended dose level requires to have at least 1** response out of 6 evaluable subjects or 2 responses out of 10 evaluable subjects **in order to proceed to Part 2.**

Part 2

For part 2, the dosing will be determined based on the safety of the combination of blinatumomab and pembrolizumab and the MTD of blinatumomab established in part 1 per DLRT. **For part 2, the DLT observation period will be determined by cohort chosen in Part 1 and Part 2 expansion.** Part 2 will consist of an expansion cohort to collect further safety and PK data as well as provide a preliminary estimate of the efficacy of the combination of blinatumomab and pembrolizumab. Dose limiting toxicities **and efficacy will be monitored by Data Review Team (DRT)** to ensure they do not reach a pre-defined threshold of 25%. If this threshold is reached, the DRT will have the discretion to change to another dose/schedule tested in phase 1b part 1, based on the totality of the available data. The details of DLT boundaries are provided in Section 8.1.

Study Design and Treatment Schema

Figure 1. Study Design and Treatment Schema

[figure not shown]

Figure Legend present on next page

DLT = dose limiting toxicity; MTD = maximum tolerated dose. First cycle of blinatumomab will be 8 weeks in duration, followed by a 28-day (\pm 3 days) blinatumomab treatment-free interval. A second consolidation cycle of blinatumomab will be 28 days in duration at the same dose as the first cycle, starting at 9 μ g/day with weekly dose escalations until the target dose is reached, if subject has stable disease or partial/complete remission after cycle 1. Pembrolizumab will be started on study day 15 for cohort Ia, and study day 19 for cohorts IIa and IIIa, and administered Q3 weeks until disease progression for up to 35 cycles. **The first dose of pembrolizumab must be delayed if blinatumomab is interrupted during the step dose period per protocol (see Table 6-1 of protocol). The first dose of pembrolizumab can only be given after the blinatumomab target dose is reached (+ 4 days); also, before adding pembrolizumab, there should be no blinatumomab dose interruption due to adverse events and if blinatumomab was interrupted, no > grade 1 CRS and/or neurologic events. The cohort name has been updated to be in sequential order, retaining the historical “a” in the cohort name (ie, cohorts Ia, IIa, IIIa) from previous protocol naming convention.**

^a For cohorts Ia, IIa and IIIa, the DLT observation period will begin on the same day as the first dose of pembrolizumab (day 15 for Ia and day 19 for IIa and IIIa) and will continue for 42 days. **For part 2, the DLT observation period will be determined by cohort chosen in Part 1 and Part 2 expansion.** A dose level review team (DLRT) will review the available data to determine if blinatumomab is safe and tolerable as defined by DLT criteria **and general clinical judgement. Based on the totality of the data, the DLRT may recommend to declare MTD, to escalate to the next dose level, to expand a cohort to a maximum of 10 subjects if the collection of more data is deemed warranted, or to adjudicate the DLT criteria.**

^b Part 1: To determine maximum tolerated dose (MTD) of blinatumomab in combination with pembrolizumab. The MTD will be defined as the dose level at which **\leq 1 DLT in 6 subjects or \leq 2 DLTs in 10 subjects** experience a Dose limiting toxicity (DLT).

^c Part 2: Expansion cohort to estimate the efficacy of the combination of blinatumomab and pembrolizumab. Dosing will be determined based on the MTD of blinatumomab established in part 1. **Dose limiting toxicities and efficacy will be monitored by the Data Review Team to ensure they do not reach a pre-defined threshold of 25%.**

^d Dosing for the Part 2 expansion cohort will be based on the safety of the combination of blinatumomab and pembrolizumab and the MTD of blinatumomab in Part 1.

3.2 Sample Size

Part 1:

A rolling 6 dose design will be used. An additional 4 subjects per cohort can be enrolled to further evaluate safety and PK data if needed. There will be a minimum of 6 subjects and a maximum of **30** subjects enrolled.

Part 2:

Forty subjects will be enrolled in Part 2. With 40 subjects, the 95% exact confidence interval (Clopper and Pearson, 1934) for the estimate of ORR can be calculated. The 95% confidence intervals for some ORRs are shown in the table below.

Table 1. Estimated 95 % Confidence Interval for ORR

ORR	95% Confidence Interval
0.40	(0.25, 0.57)
0.45	(0.29, 0.61)
0.50	(0.34, 0.71)
0.55	(0.38, 0.71)
0.60	(0.43, 0.75)

4. Study Endpoints and Covariates

4.1 Study Endpoints

4.1.1 Primary Endpoints

- Incidence of DLTs

4.1.2 Secondary Endpoints

- **Objective response** (including CR and PR) by the **Lugano Classification (Cheson et al, 2014) and Revised Response Criteria (Cheson et al, 2007) during the first 12 weeks since starting blinatumomab and during the treatment period.**
- **Complete response** by the **Lugano Classification (Cheson et al, 2014) and Revised Response Criteria (Cheson et al, 2007) during the first 12 weeks since starting blinatumomab and during the treatment period.**
- PFS
- OS
- Duration of response (DOR) **for subjects with OR, (ie, CR and PR) by the Lugano Classification (Cheson et al, 2014) and Revised Response Criteria (Cheson et al, 2007) during the first 12 weeks since starting blinatumomab**
- Blinatumomab PK parameters
- Pembrolizumab PK parameters

4.1.3 Safety Endpoints

- Incidence and severity of adverse events

4.1.4 Exploratory Endpoints

- **Tumor PD-L1 expression will be assessed pre-treatment and on treatment to explore potential correlation with clinical outcomes**
- Changes in Lymphocytes (B-cell, T-cell populations, NK cells) and leukocyte populations (leukocytes, lymphocytes, monocytes, and granulocytes) in peripheral blood
- Peripheral blood cytokine levels
- Minimal residual disease (MRD) by NGS after cycle 1 of blinatumomab

5. Hypotheses and/or Estimations

The overlying hypothesis is that blinatumomab in combination with pembrolizumab will be tolerable in r/r DLBCL.

6. Definitions

6.1 General Definitions

Age at Enrollment

Subject age at enrollment will be collected in years in the clinical database.

Baseline

For the analysis of all endpoints, baseline will be defined as the value measured on day 1 of the first cycle of blinatumomab. The protocol specifies that procedures and labs on day 1 should be completed before the initiation of any protocol-specified therapy which will be the assumption in the analysis unless the time of the assessment is recorded. If a day 1 value is not available, the most recent value before the day of the start of any protocol-specified therapy may be used.

Cumulative Dose of Blinatumomab, Pembrolizumab

Blinatumomab: The cumulative dose in μg is defined as the following with summation over infusions:

$$\sum (\text{Duration of infusion (days) for each dose received} \times \text{dose received } [\mu\text{g}])$$

Pembrolizumab: The cumulative dose in mg is defined as the following with summation over infusions:

$$\sum (\text{Duration of infusion (days) for each dose received} \times \text{dose received } [\text{mg}])$$

Cumulative dose will be calculated within a cycle and across all cycles.

Death Date

For subjects who die during the study, the death date will be recorded on the event, end of study and survival status CRF. The earliest date will be used if the dates are inconsistent among these CRF pages. For deaths collected after a subject has ended study (eg, through public records in countries where permitted), the death date will be recorded on the long term follow-up page.

Dose limiting toxicity (DLT)

The occurrence of any of the toxicities in the Appendix E of the protocol will be considered a DLT, if judged by the investigator to be possibly, probably or definitely related to study drug administration.

DLT Evaluable

To be DLT evaluable, subjects must meet one of the following criteria during DLT evaluation period:

- The subject experienced a DLT;

OR

- The subject was removed from treatment for an adverse event/toxicity **that is not a DLT, if the subject has been exposed to both investigational products for at least 12 days since pembrolizumab initiation with blinatumomab at the target dose;**

OR

- The subject was removed from treatment for reasons other than an adverse event/toxicity (ie, disease progression), and the subject has **been exposed to both investigational products for at least 12 days since pembrolizumab initiation** with blinatumomab at the target dose;

OR

- The subject did not experience a DLT and completed the DLT **evaluation** period.

Duration of Blinatumomab/Pembrolizumab

Blinatumomab/ Pembrolizumab: For each infusion episode within a cycle, the duration of exposure will be calculated by subtracting the start date and time from the stop date and time. If either a start or stop time is missing, only the date portion will be used in calculating the duration of a specific infusion. For each cycle, the duration will be last date minus first date plus 1 of infusion. For the entire study, the duration will be the sum of the durations across cycles. The duration will be rounded to the nearest day.

Event of Clinical Interest (ECI)

Selected non-serious and serious adverse events are known as ECI and must be reported within 24 hours to the sponsor. The ECI for this trial includes

- An overdose of blinatumomab or pembrolizumab (see Protocol Section 6.2.1.1 and Section 6.2.2.1)
- Hepatic disorder (See protocol section 9.1.4)

Events of interest (EOI)

Events of interest (EOI) will be based on search strategies defined by Standard MedDRA Queries (SMQs) or Amgen MedDRA Queries (AMQs).

End of Investigational Product (IP) Administration Date

End of IP Administration for subjects who had blinatumomab or pembrolizumab is defined as the last infusion of blinatumomab/ pembrolizumab reported on the End of IP Administration CRF.

Enrollment Date

Enrollment Date is defined as the date of enrollment collected on the CRF.

Investigational Product

Amgen Investigational Product: refers to blinatumomab

Non-Amgen Investigational Product: refers to pembrolizumab

Last Dose Date of Blinatumomab/ Pembrolizumab

This is the stop date of the last infusion of blinatumomab/pembrolizumab administration reported on the Investigational Product Administration CRF.

Treatment period

Treatment period will be from study day 1 to 30 days after last dose of either blinatumomab/ pembrolizumab administration reported on the Investigational Product Administration CRF.

Prior Salvage Regimens

Prior salvage regimens are those medications recorded on the prior anti-cancer therapies CRF where the line of therapy field indicates 2nd or higher line therapy.

Relative Dose Intensity at the Target Dose

Relative dose intensity at the target dose is the actual exposure duration at target dose divided by planned duration of target dose, which is 49 days for cohort Ia, and 42 days for cohort IIa and IIIa in cycle 1; and 21 days for cohort Ia, and 14 days for cohort IIa and IIIa in cycle 2. Subjects who didn't reach the target dose are considered having actual exposure duration as 0.

Study Day

Study Day 1 is defined as the day of first dose of blinatumomab.

And Study Day is defined as:

Pre study day 1: study day= (date – date of study day 1)

Post study day 1: study day= (date - date of study day 1) + 1

Subject Level End of Study (EOS) Date

End of Study for each subject is defined as the date the subject last completed a protocol-specified procedure. The date will be recorded on the End of Study CRF page.

Treatment Emergent Adverse Event (AE)

Treatment emergent adverse event refers to an adverse event that starts on or after first dose of blinatumomab up to and including 30 days after the end of blinatumomab or pembrolizumab whichever is later. It is indicated by a flag whether an event start before first dose of blinatumomab on the Event CRF page. This reporting window also applies to treatment-emergent serious adverse events (SAEs).

Treatment Emergent Disease-related Event (DRE)

Treatment emergent disease-related event refers to a disease-related event that starts on or after first dose of blinatumomab up to and including 30 days after the end of blinatumomab or pembrolizumab whichever is later. It is indicated by a flag whether an event start before first dose of blinatumomab on the Event CRF page.

Disease-related events assessed by the investigator to be more severe than expected and/or related to the investigational product(s)/study treatment/protocol-required therapies, and determined to be serious, must be reported on the Event CRF as serious adverse events.

Treatment Emergent Event of Clinical Interest (ECI)

ECI is defined in Section 9.1.4 of the protocol. Treatment emergent ECI refers to an ECI that starts on or after first dose of blinatumomab up to and including 30 days after the end of blinatumomab or pembrolizumab whichever is later.

Primary Completion: The primary completion date is defined as the date when the last subject is assessed or receives an intervention for the final collection of data for the primary endpoint(s), whether the study concluded as planned in the protocol or was terminated early.

If the study concludes prior to the primary completion date originally planned in the protocol (ie, early termination of the study), then the primary completion will be the date when the last subject is assessed or receives an intervention for evaluation in the study (ie, last subject last visit).

The primary completion date is the date when data for the primary endpoint are last collected for the purposes of conducting the primary analysis.

End of Study: The end of study date is defined as the date when the last subject across all sites is assessed or receives an intervention for evaluation in the study (ie, last subject last visit), following any additional parts in the study (eg, long-term follow-up) as applicable.

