For blinatumomab, a dose of greater than 10% higher than the intended dose will be considered clinically important and classified as a serious adverse event under the criterion of “other medically important serious event” per Section 9.1.3. If the overdose results in additional adverse event/s, the subject should be followed carefully until all signs of toxicity are resolved and the adverse event/s should be recorded/reported per Section 9.2 of the protocol.

The dose, start and stop date/time, and lot number of protocol-specified therapy is to be recorded on each subject’s CRF.

Refer to the Blinatumomab Investigational Brochure for further information.

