6.2.2.1 Pembrolizumab Dosage, Administration, and Schedule

Trial treatment should begin as close as possible to the date on which the subject is allocated/assigned. The pembrolizumab treatment to be used in this trial is outlined below in [Table 6-2](#).

Schedule of pembrolizumab dosing and related assessments for cohort Ia are provided in [Table 7-1](#) and [Table 7-2](#), and for cohorts IIa and IIIa are provided in [Table 7-3](#) and [Table 7-4](#). Pembrolizumab will be administered as a dose of 200 mg using a 30-minute IV infusion. Sites should make every effort to target infusion timing to be as close to 30 minutes as possible. However, given the variability of infusion pumps from site to site, a window between - 5 minutes and + 10 minutes is permitted (ie, infusion time is 30 minutes - 5 minutes/+ 10 minutes).

For this trial, an overdose of pembrolizumab will be defined as ≥ 1000 mg (5 times the dose) of pembrolizumab. No specific information is available on the treatment of overdose of pembrolizumab. In the event of overdose of pembrolizumab, the subject should be observed closely for signs of toxicity. Appropriate supportive treatment should be provided if clinically indicated.

Table 6-2. Trial Treatment

Drug	Dose/ Potency	Dose Frequency	Maximum Length of Dosing	Route of Administration	Regimen ^a	Use
Pembrolizumab	200 mg	Every 21 days	Up to 35 cycles	Intravenous	First dose starting at study day 15 (cohort Ia), and study day 19 (cohorts IIa and IIIa) (21-day cycles)	Experimental

^a Starting from pembrolizumab cycle 2, pembrolizumab may be administered ± 3 days from the planned dosing day.

6.2.2.2 Dosage Adjustments, Delays, Rules for Withholding or Restarting, Permanent Discontinuation for Pembrolizumab

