10.6.8 Exposure to Investigational Product

Descriptive statistics will be produced to describe the exposure to blinatumomab and pembrolizumab. The number of cycles initiated, completed, discontinued, and re-started of blinatumomab and pembrolizumab will be summarized. **If a subject completed 85% of planned days on target dose, he/she is considered as completing a cycle.** In addition, the duration of therapy will be summarized by cycle and overall. **Relative dose intensity at the target dose will be calculated. It is the actual exposure duration at target dose divided by planned duration of target dose, which is 49 days for cohort Ia, and 42 days for cohort IIa and IIIa in cycle 1; and 21 days for cohort Ia, and 14 days for cohort IIa and IIIa in cycle 2. Subjects who didn't reach the target dose are considered having actual exposure duration as 0. Relative dose intensity at the target dose will be summarized by cycle.** The number and percent of subjects with dose modifications (eg, dose changes, dose interruptions) and reasons for modification will be summarized. **Analysis will be performed based on Safety Analysis Set.**

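### SAP 6.1 multiplies pembrolizumab mg by infusion time in days, so a 200 mg dose is recorded as about 4 instead of 200

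*SAP*

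**What the plan says.** SAP 6.1 (General Definitions) defines cumulative dose for both drugs with the same formula. For pembrolizumab the lead-in is "Pembrolizumab: The cumulative dose in mg is defined as the following with summation over infusions", and the term summed is "Duration of infusion (days) for each dose received" multiplied by the dose received in mg. The blinatumomab formula directly above it differs only in using µg. The SAP commits to calculating the variable per cycle and over all cycles.

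The SAP 6.1 entry on duration covers both drugs and contains several rules:

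- For a single infusion, duration is stop date and time minus start date and time.
- For incomplete times, "If either a start or stop time is missing, only the date portion will be used in calculating the duration of a specific infusion".
- At cycle level, "For each cycle, the duration will be last date minus first date plus 1 of infusion".
- After the sentence on whole-study duration, the entry ends with "The duration will be rounded to the nearest day".

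On dosing, Protocol 6.2.2.1 says "Pembrolizumab will be administered as a dose of 200 mg using a 30-minute IV infusion" and allows 5 minutes less or 10 minutes more. Table 6-2 caps treatment at 35 cycles of 21 days. Protocol 3.1 and 6.2.1.1 state blinatumomab doses in µg/day.

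On outputs, SAP 10.6.8 says "Descriptive statistics will be produced to describe the exposure to blinatumomab and pembrolizumab".

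**The concern.** Duration times dose gives an amount only when the dose is a rate. Blinatumomab is a continuous infusion prescribed per day, so days × µg/day gives µg. Pembrolizumab's 200 mg is already the amount for the whole infusion. Multiplying it by the infusion's length in days gives mg-days, although the definition labels the result as mg.

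Two things follow. Programmed literally, the variable is far below the mg received and depends on pump speed, so subjects given identical doses would have different values. The formula also does not say which SAP 6.1 duration rule supplies the multiplier, so two programmers could defensibly produce different results. What is at stake is the correctness of a descriptive exposure variable.

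**Working it through.** The SAP prints no numerical cumulative dose, so there is no figure of its own to reproduce. The check applies the formula to one standard infusion under each duration rule.

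**Inputs**

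- Dose: 200 mg (Protocol 6.2.2.1).
- Infusion length: 30 minutes, allowed range 25 to 40 (Protocol 6.2.2.1).
- Maximum infusions: 35, one per cycle (Protocol Table 6-2).
- Formula: sum over infusions of duration in days × dose in mg (SAP 6.1).
- Assumption: each infusion starts and ends on the same calendar date.

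**One 200 mg infusion**

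| Duration rule (SAP 6.1) | Duration, days | Result |
|---|---|---|
| Stop minus start, unrounded, 30 min | 30/1440 = 0.0208 | 200 × 30/1440 = 4.17 |
| Same, 25 min | 25/1440 = 0.0174 | 200 × 25/1440 = 3.47 |
| Same, 40 min | 40/1440 = 0.0278 | 200 × 40/1440 = 5.56 |
| Clock time missing, dates only | 0 | 0 |
| Rounded to the nearest day per infusion | 0.0208 rounds to 0 | 0 |
| Cycle level, last minus first date plus 1 | 1 | 200 |

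The first row is the literal reading, because the formula names infusion duration and sums over infusions. At 30 minutes it understates the dose by a factor of 1440/30 = 48.

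**Thirty-five infusions**

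- Amount given: 35 × 200 = 7000 mg.
- Literal reading at 30 minutes: 35 × 200 × 30/1440 = 145.8.
- Literal reading over the allowed window: 35 × 200 × 25/1440 = 121.5 to 35 × 200 × 40/1440 = 194.4.
- Dates only, or per-infusion rounding: 0.
- Cycle-level rule: 35 × 1 × 200 = 7000.

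The cycle-level result matches the amount given only because multiplying by 1 leaves the dose unchanged.

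**The same formula for blinatumomab**

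In cohort Ia, cycle 1 is 7 days at 9 µg/day followed by the 49 planned target-dose days in SAP 6.1 at 28 µg/day: 7 × 9 + 49 × 28 = 63 + 1372 = 1435 µg. The formula works here, but only if the dose term is µg/day. The SAP labels it µg.

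**The case against.** The strongest reply is that little depends on this. SAP 10.6.8 lists cycles started, completed, discontinued and re-started, duration of therapy, relative dose intensity and dose modifications. It does not name cumulative dose, and neither does the matching list in Protocol 10.4.2.3. Because the dose is fixed and Table 6-3 provides for continuing, withholding or stopping pembrolizumab but not for reducing it, the mg received can largely be recovered from the number of cycles started. This stands, and it keeps the point minor. It does not remove it: SAP 6.1 still says the variable will be calculated, and an infusion stopped early for a reaction (Protocol Table 14-1) makes a cycle count an imperfect substitute.

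A second reply is that the possible results do not carry equal weight. This also stands. A missing clock time should be uncommon, since the protocol requires start and stop times to be recorded. The rounding sentence follows the whole-study duration, so rounding each infusion first is a weak reading. The 200 needs a cycle-level rule that the formula does not cite. The firm result is therefore 4.17, and a programmer who counted whole days per cycle would happen to get the right number.

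Third, 35 infusions is the maximum, since treatment stops at progression or relapse, so the per-infusion ratio says more than the 7000 mg contrast. Fourth, the blinatumomab label can be read as shorthand, because its doses are given per day throughout. Both are fair; the blinatumomab point is only a labelling correction.

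**Conclusion.** The concern holds, as a minor error of definition and units. Followed as written, SAP 6.1 gives 4.17 for a 200 mg, 30-minute infusion (3.47 to 5.56 over the allowed window), and the value rises with infusion time at a constant dose. Neither the rest of SAP 6.1 nor SAP 10.6.8 contains a pembrolizumab exception that corrects it.

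The figures assume full 200 mg infusions, one per cycle, each within a single calendar day. The effect is confined to this variable and any descriptive summary that uses it. DLT, efficacy, relative dose intensity and concentration-based pharmacokinetic results are untouched.

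**What to change.** In SAP 6.1, define pembrolizumab cumulative dose as the sum over infusions of the mg actually administered, taken from the Investigational Product Administration CRF, with no duration term. One full infusion then gives 200 mg and 35 give 7000 mg.

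Keep duration × dose for blinatumomab only, label its dose term µg/day, and state that the multiplier is the unrounded infusion-level duration.

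The cost is one or two lines of SAP text. No new data are needed. Protocol 6.2.1.1 already requires that "The dose, start and stop date/time, and lot number of protocol-specified therapy is to be recorded" on the CRF, and Protocol Section 6 defines protocol-specified therapies as both blinatumomab and pembrolizumab.
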